5. STUDY TREATMENT REGIMEN

Please refer to Section 1.5 and to applicable package inserts and product labeling for known and potential risks to human subjects associated with the study treatment regimen.

Table 1. Islet Transplant and Immunosuppression Regimen

	Days Relative to Transplant												
	-2	-1	0	1	2	3	4	5	6	7	10	14	21
Islet Transplant			X										
ATG (Initial Transplant Only)	X	X	X	X	X								
Basiliximab (Subsequent Transplants Only)			X				X						
AAT			X										AAT will be given on Monday, Wednesday, Friday schedule for total of 9 doses in 3 weeks
Etanercept			X				X				X	X	

5.1 Investigational Agent: GLASSIA

GLASSIA is human alpha1 proteinase inhibitor indicated in patients with lung disease secondary to severe hereditary deficiency of alpha1-antitrypsin (AAT). For this purpose the recommended dose for chronic therapy is 30 mg/kg once weekly at a rate of 0.2 ml/kg/min via iv infusion. In the current trial, patients will receive a 90 mg/kg load followed by 30mg/kg 3x/week for 3 weeks. It should take approximately 30 minutes to infuse. Its use is contraindicated in patients with IgA deficiency with anti-IgA antibodies as this may result in severe hypersensitivity and or anaphylaxis. GLASSIA is pregnancy category C.

5.1.1 Formulation, Dosing, Administration and Emergency Precautions

GLASSIA (Kamada) is available commercially as a ready to use, liquid preparation of purified human-alpha₁-protease inhibitor (Alpha₁-PI). It is prepared from human plasma though cold ethanol fractionation. GLASSIA is available in with UPS Water for Injection (to 1 gm/50ml).

The first dose of GLASSIA will be calculated with the recipients body weight recorded during the admission for transplant. Subsequent doses will be calculated using the weight recorded on the admission for that dosing. The dose will be rounded to the nearest whole vial dose but must be within

10% of calculated dose. Patients will receive a loading dose of 90 mg/kg followed by maintenance dose of 30mg/kg/dose. A trough level will be measured between 2nd and 3rd dose. If the AAT level is not between 2.5-3.5 mg/ml we will increase dose to 60mg/kg/dose for the remaining doses.

GLASSIA will be used within three hours per package insert guidelines. The infusion will be administered by a qualified individual, using a 5 micron in-line filter during the infusion. Vital signs will be recorded within 30 minutes before initiating the infusion and every 30 minutes during the infusion and within 15 minutes after completing the infusion.

With each infusion, medical personnel will be available to treat subjects who experience anaphylaxis. Emergency treatment such as 0.3 mL to 0.5 mL aqueous epinephrine (1:1000 dilution) subcutaneously and other resuscitative measures including oxygen, IV fluids, antihistamines, corticosteroids, pressor amines, and airway management, as clinically indicated, should be provided.

5.1.2 Drug Accountability

Under Title 21 of the Code of Federal Regulations (21CFR §312.62), the investigator is required to maintain adequate records of the disposition of the investigational agent, including the date and quantity of the drug received, to whom the drug was dispensed (subject-by-subject accounting), and a detailed accounting of any drug accidentally or deliberately destroyed.

Records for receipt, storage, use, and disposition will be maintained by the study site. A drug-dispensing log will be kept current for each subject. This log will contain the identification of each subject and the date and quantity of drug dispensed.

All records regarding the disposition of the investigational product will be available for inspection by the clinical trial monitor.

At the end of the each islet infusion, we plan to transplant a small fraction of the total islet mass (~2-3%) into the abdominal wall subcutaneous tissue or preperitoneal space at the time of portal infusion into at least 4 discrete locations marked by a suture or surgical clip. We estimate that 8,000-10,000 islets of a 400,000-500,000 islet preparation are placed in this location (2000-2500 islets per pocket in 0.5 ml of collagen emulsion (Cosmoderm)), the auxiliary graft will readily allow us to obtain a sizeable biopsy of hundreds to thousands of islets for microscopic evaluation rather than an occasional one or two islets seen with liver core biopsy. Since we plan to transplant islets via mini-laparotomy, this will not add surgical morbidity or risk to the procedure. By marking the location of sites with radio-opaque clips, we will be able to biopsy the site under local anesthesia in the OR at any time post transplant. It is conceivable that subcutaneous islets could be more immunogenic than those in the liver and could even trigger rejection of the islet mass in the liver. Although it is difficult to estimate this risk, we assume it is very low and will include this risk in the patient's consent. In addition, the consent will be written in such a way to allow study candidates to opt in or out for this proportion of the procedure.

5.2.2 Drug Accountability

Under Title 21 of the Code of Federal Regulations (21CFR §312.62), the investigator is required to maintain adequate records of the disposition of the investigational agent, including the date and quantity of the drug received, to whom the drug was dispensed (subject-by-subject accounting), and a detailed accounting of any drug accidentally or deliberately destroyed.

Records for receipt, storage, use, and disposition will be maintained by the study site. A drug-dispensing log will be kept current for each subject. This log will contain the identification of each subject and the date and quantity of drug dispensed.

All records regarding the disposition of the investigational product will be available for inspection by the clinical trial monitor.

5.3 Immunosuppression Medications

5.3.1 Initial Allogeneic Islet Transplant

Please refer to applicable product labeling and Package Inserts for known and potential risks to human subjects associated with the standard immunosuppressive medications.

RABBIT ANTI-THYMOCYTE GLOBULIN (THYMOGLOBULIN®)

A total of 6 mg/kg will be given as an IV infusion on days -2, -1, 0, +1, and +2. The dose will be 1.5 mg/kg on day -2, 1.0 mg/kg on day -1, and 1.5 mg/kg on days 0, +1, and +2. The doses will be administered as directed on the package insert and in the CIT-06 Manual of Procedures. The dose will be limited to 3 mg/kg total (0.5mg/kg on day -2, 1.0 mg/kg on day -1 and 1.5mg/kg on day 0) in patients treated with depleting antibody induction therapy (hOKT3y1 ala-ala, rabbit ATG, or Campath®) for their renal transplant within the last year. Patients previously treated with rabbit ATG will be tested for efficacy day - 2 relative to the islet transplant by assessment of T cell depletion by CD3 counts measured after administration of the first ATG dose. If lack of efficacy is detected, basiliximab

(Simulect®) can be substituted for rabbit ATG using the regimen detailed below for subsequent transplants. Premedications will be used as follows:

1. Acetaminophen (Tylenol®) 650 mg PO/PR ½ hr before and midway through ATG infusion
2. Diphenhydramine (Benadryl®) 50 mg PO ½ hr before and midway through ATG infusion
3. Methylprednisolone (Solu-Medrol®) 1 mg/kg IV one hour prior to and as needed through the first ATG infusion only (*i.e.* on day –2)
4. Pentoxifylline (Trental®) 400 mg PO TID to be initiated one hour prior to the first ATG infusion and to be continued through day +7

If the subject is admitted when the vascular access team is not available or at a time when the placement of a PICC could delay the first rabbit ATG dose it may be administered IV via a peripheral line as follows:

- Dilute the rabbit ATG in 500 cc Normal Saline (not D5W)
- Combine with Heparin 1000 units and Hydrocortisone 20 mg.

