
I confirm that I have read the above protocol in the latest version. I understand it, and I will work according to the principles of current Good Clinical Practice (cGCP) as described in the United States Code of Federal Regulations (CFR) – 21 CFR Parts 45, 50, 56, and 312, and the International Conference on Harmonization (ICH) document “Guidance for Industry: E6 Good Clinical Practice: Consolidated Guidance” dated April 1996. Further, I will conduct the study in accordance with local, legal, and regulatory requirements.
 
As the site Principal Investigator, I agree to conduct protocol, “Efficacy of AAT in Islet after Kidney Transplantation,” according to good clinical practices. I agree to carry out the study by the criteria written in the protocol and understand that no changes can be made to this protocol without written permission of the sponsor.
 <hr/> 
Site Principal Investigator (Print)
 <hr/> 
Site Principal Investigator (Signature)
 
Date
	

Protocol Synopsis

Title	Multicenter Trial of the effect of AAT on Islet Transplant Engraftment and Durability after Renal Transplant
Short Title	Efficacy of AAT in Islet after Kidney Transplantation
Clinical Phase	Phase 2
IND Sponsor	[name]
IND Number	BB-IND 13804
Activation Date	Proposed 12/2016
Accrual Objective	20 transplanted (up to 28 transplant eligible)
Accrual Period	3 years
Study Duration	5 years (Accrual plus follow-up)
Study Design	Prospective, multi-center, trial assessing the benefit of alpha-1 antitrypsin (AAT) on islet transplantation in type 1 diabetic (T1D) kidney transplant recipients.
Treatment Description	Patients meeting the study entry criteria will receive 1-3 infusion(s) of in vitro cultured islets. Patients will receive three times a week AAT infusions in the peri-transplant period for three weeks. For the first islet transplant, patients will receive induction therapy with rabbit anti-thymocyte globulin (ATG, 6 mg/kg total in 5 doses) plus etanercept and will remain on their calcineurin-based maintenance immunosuppression regimen already in place for their renal allograft. Induction therapy will be basiliximab instead of ATG for 2 nd and 3 rd transplants, if applicable.

Primary Endpoints

The proportion of GLASSIA versus control subjects from CIT-06 achieving insulin independence at day 75 after the first infusion of single donor islets.

Secondary Endpoints

Insulin Utilization

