1.3.3 Immunosuppressive Medications for Initial Islet Transplant

1.3.3.1 Rabbit Anti-Thymocyte Globulin (Thymoglobulin®)

Rabbit ATG is a polyclonal antibody preparation that depletes T and B cells following IV administration^{28, 81-85}. It is approved by the Food and Drug Administration (FDA) for treatment of rejection in kidney transplant recipients receiving adjunctive immunosuppression. It will be administered IV on day -2 (0.5 mg/kg), -1 (1 mg/kg), 0, 1, and +2 (1.5 mg/kg/dose). The dose will be limited to 3 mg/kg total (0.5mg/kg on day -2, 1.0 mg/kg on day -1 and 1.5mg/kg on day 0), in patients treated with depleting antibody induction therapy (hOKT3y1 ala-ala, rabbit ATG, or Campath) for their renal transplant within the last year. Patients previously treated with rabbit ATG will be tested for efficacy on day -2 relative to the planned islet transplant by assessment of T cell depletion by CD3 (total T lymphocyte) counts measured after administration of the first ATG dose. If lack of efficacy is detected, basiliximab (Simulect®) can be substituted for rabbit ATG using the

regimen detailed below for subsequent transplants. Methylprednisolone, acetaminophen, pentoxifylline, and diphenhydramine will be administered as premedications 1 hour prior to the first dose of rabbit ATG.

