We have paired GLASSIA with what has become the standard for immunosuppression in islet transplantation based on the recent work of the CIT and the seminal studies of Hering et al who reported what are arguably the most successful series of islet-alone transplants using potent induction immunosuppression and high quality islets. In a series of 10 consecutive patients treated with rabbit ATG induction therapy (6 mg/kg total dose), 9 became insulin independent with a single infusion of islets⁹². The patient who did not become insulin independent had the benefit of a reduced insulin requirement to 4 U/day. No SAEs have been observed.

Based on these data, the CIT adopted the regimen based on Thymoglobulin induction combined with a brief course of Etanercept the soluble form of the p75 receptor for TNF (etanercept). Etanercept is a dimeric fusion protein consisting of the extracellular ligand- binding portion of the human 75 kilodalton (p75) TNF receptor linked to the constant fraction (Fc) portion of human IgG1. Etanercept inhibits binding of both TNF- α and TNF- β to cell surface TNF receptors, rendering TNF biologically inactive. It is well recognized that TNF- α and TNF- β play multiple roles in the development and function of the immune system and have pleomorphic regulatory effects on the development and expression of autoimmunity⁹³. Blockade of TNF in the neonatal period results in a dramatic increase in the levels of CD4+CD25+ regulatory T cells in NOD mice^{94, 95}.

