Rabbit ATG has been found to be more effective at preventing rejection compared to an anti-IL- 2 receptor agent (basiliximab) in a randomized multi-center kidney transplant trial including sites in the US and Europe^{85, 99}. The incidence of rejection was 1.8 times higher in patients receiving a standard 2-dose course of basiliximab compared with a 5-day induction with rabbit ATG (1.5 mg/kg/day). The rate of AEs, SAEs, and infections was similar between groups. In addition, in large registry studies, the incidence of post-transplant lymphoproliferative disease (PTLD) in rabbit ATG treated patients was quite low (0.3 to 0.5%)¹⁰⁰.

The current protocol plans to rely on the CIT backbone regimen of rabbit ATG and Etanercept to allow us to assess whether the addition of GLASSIA improves initial engraftment and long-term survival.

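### Section 5.3.1's daily rabbit ATG doses sum to 7.0 mg/kg against a stated 6, and Section 7.6.1 stops immunosuppression after second islet-graft failure with no exception for the kidney graft

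*Combined protocol and SAP*

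**What the plan says.** **ATG.** Section 5.3.1 first gives the total: "A total of 6 mg/kg will be given as an IV infusion on days -2, -1, 0, +1, and +2". The next sentence gives the daily doses: "The dose will be 1.5 mg/kg on day -2, 1.0 mg/kg on day -1, and 1.5 mg/kg on days 0, +1, and +2". For patients who had depleting induction with their kidney transplant within the last year, the same paragraph adds: "The dose will be limited to 3 mg/kg total (0.5mg/kg on day -2, 1.0 mg/kg on day -1 and 1.5mg/kg on day 0". In patients previously given rabbit ATG, efficacy is judged by "assessment of T cell depletion by CD3 counts measured after administration of the first ATG dose", and basiliximab may replace ATG if efficacy is lacking. Section 1.3.3.1 gives a different schedule: "It will be administered IV on day -2 (0.5 mg/kg), -1 (1 mg/kg), 0, 1, and +2 (1.5 mg/kg/dose". The synopsis gives "rabbit anti-thymocyte globulin (ATG, 6 mg/kg total in 5 doses". Table 1 marks the five ATG days but no doses.

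**Withdrawal.** The last sentence of Section 7.6.1 classes recipients whose graft fails after the second islet transplant as treatment failures and says that their immunosuppression is to be withdrawn. It names no drugs and makes no exception. Under inclusion criterion 6 (Section 3.1), every subject has a kidney transplant and takes calcineurin-inhibitor-based maintenance. Section 1.5.1.3 describes stopping as usual in islet-alone patients and says that kidney recipients carry on with maintenance even when the islets fail. Section 1.5.6 says that the regimen in place for the kidney will continue. Section 5.8.2 (graft failure) keeps that regimen for as long as another islet transplant is possible; after that it mentions only the move to reduced follow-up.

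**The concern.** A site cannot comply with both the total and the daily doses in 5.3.1. One that works from the daily line gives an unintended first dose, and sites may resolve the conflict differently. Two features depend on uniform dosing. Section 4.1 presents the trial as following the CIT-06 treatment regimen except for GLASSIA and related mechanistic studies, and CIT-06 supplies the controls. The CD3 check, which can trigger the switch to basiliximab, is also read after that first dose.

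The withdrawal rule carries the greater risk. Taken literally, it stops the drugs that protect a working kidney graft in someone who has just lost an islet graft. Section 7.6.1 is where a site would look for what to do at that moment; the statements that renal maintenance continues after islet failure sit in the background and risk text.

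**Working it through.** **ATG totals** (mg/kg, days -2, -1, 0, +1, +2)

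| Source | Daily doses | Sum | Stated total |
|---|---|---|---|
| 5.3.1, full regimen | 1.5 + 1.0 + 1.5 + 1.5 + 1.5 | 7.0 | 6 |
| 1.3.3.1, full regimen | 0.5 + 1.0 + 1.5 + 1.5 + 1.5 | 6.0 | none in that section; synopsis 6 |
| 5.3.1, reduced regimen | 0.5 + 1.0 + 1.5 | 3.0 | 3 |

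The stated 6 mg/kg is not reproduced from the doses in 5.3.1. It is reproduced from 1.3.3.1.

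*Which figure is the slip?* The two full schedules differ only on day -2. With 0.5 there, 5.3.1 agrees with its own total, with 1.3.3.1 and with the synopsis. The reduced regimen also opens at 0.5; with 1.5 it would total 1.5 + 1.0 + 1.5 = 4.0, not 3. Section 1.4 gives the same total for the series that led to the CIT regimen: "treated with rabbit ATG induction therapy (6 mg/kg total dose". Keeping 1.5 on day -2 would mean that 1.3.3.1, the synopsis and the total in 5.3.1 are all wrong.

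*Size.* Total: 7.0/6.0 = 1.167, or +17%. First dose: 1.5/0.5 = 3-fold. The extra 1.0 mg/kg is 50, 70 or 90 mg at 50, 70 or 90 kg; 90 kg is the weight limit in Section 3.2, and the other two weights are assumptions.

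*Context.* Section 1.4 describes a kidney trial whose basiliximab arm was "compared with a 5-day induction with rabbit ATG (1.5 mg/kg/day": 5 × 1.5 = 7.5 mg/kg, and 7.0/7.5 = 0.93. Section 1.5.3.2 describes 1.5 mg/kg/day for 7 to 14 days in 82 kidney recipients: 10.5 to 21 mg/kg.

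*CD3 check.* Patients on the reduced regimen already receive 0.5 mg/kg on day -2, so the slip does not reach them. It affects only patients with earlier rabbit ATG who are outside that regimen; as printed they would be tested after 1.5 mg/kg.

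**Withdrawal**

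1. What could 7.6.1 be stopping? ATG is a five-day course at the first transplant, basiliximab is given on days 0 and 4, and etanercept ends on day +10 (Sections 5.3 and 5.4.1). Once those days have passed, kidney maintenance is the only continuing immunosuppression.
2. Does 5.8.2 prevent it? Its protection lasts while another islet transplant is possible. Section 7.6.2 requires partial graft function at one month for a third transplant, and 7.6.1 classes these subjects as treatment failures, so the condition will usually have ended.
3. Does 5.8.3 prevent it? It links ending chronic immunosuppression to loss of the kidney. That implies the right answer without overriding 7.6.1.
4. Sections 1.5.1.3 and 1.5.6 contradict the literal rule.

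**The case against.** On ATG, the correct total stands in the sentence before the faulty one and again in the synopsis, so a pharmacist may see the conflict. The dose in 5.3.1 is to be given as directed in the CIT-06 Manual of Procedures, which is not among the documents. No CD3 threshold is given, so no change in the basiliximab decision can be shown, nor any effect on the comparison with CIT-06. All of this stands. It lowers the priority of the correction and means that 0.5 mg/kg is the most likely reading, not a certain one.

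A reader might infer that 5.3.1 orders a toxic dose. The documents do not support that: the literal 7.0 mg/kg is below both courses shown above. Section 1.4 reports similar adverse event, serious adverse event and infection rates for its ATG and basiliximab arms, and the first-dose infusion safeguards in 5.8.2 apply at either dose. A reader might also infer that the CD3 check is distorted in everyone with prior ATG; the reduced regimen rules that out.

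On withdrawal, the contrary text is substantial. The synopsis and Sections 4 and 7.4 keep subjects on calcineurin-based maintenance. Section 1.2 treats immunosuppression as lifelong in these patients. Section 5.8.2 puts the kidney first when drugs are not tolerated, and 5.8.3 dates study treatment from the first induction dose, which arguably leaves renal maintenance outside it. An experienced transplant team is unlikely to act on the sentence literally. It would therefore be wrong to infer that the plan intends to stop the kidney drugs. But 7.6.1 speaks of immunosuppression, not study treatment, and none of these passages says that it does not apply. A clinician who rightly continues the drugs would be departing from the written rule.

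**Conclusion.** Both rules are wrong as written.

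- **Withdrawal (7.6.1, with the condition in 5.8.2): must fix, for safety.** All 20 planned subjects would have a kidney graft. How many would have second islet-graft failure cannot be estimated from the documents.
- **ATG (5.3.1): should fix.** The schedule exceeds its stated total by 1.0 mg/kg (+17%), and the first dose is three times the likely intended one. It affects up to 20 subjects, less those on the reduced regimen, whose number is not given. The conclusion that day -2 should be 0.5 mg/kg rests on agreement within the protocol and still needs the manual check.

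Neither point changes power, endpoints or analysis.

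**What to change.** Issue one clarifying amendment with a letter to sites:

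1. **5.3.1:** change the day -2 dose from 1.5 to 0.5 mg/kg, after confirming it against the CIT-06 Manual of Procedures.
2. **7.6.1:** state that after second islet-graft failure only islet-directed therapy stops, and that renal maintenance immunosuppression continues.
3. **5.8.2, graft failure:** remove the condition that ties the renal regimen to the possibility of another islet transplant.

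The unit of the AAT infusion rate in Section 4 can be verified at the same time: it is printed per minute, whereas 5.1 gives the labelled rate per kg per minute.

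The cost is the amendment and the letter. Sample size, endpoints and analysis stay as they are.

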5.3.2 Subsequent Allogeneic Islet Transplants and Second Attempts at Initial Transplants

The immunosuppressive regimen for subsequent islet transplants and second attempts at initial transplant will be identical to the regimen for the initial islet transplant with the following exceptions.

BASILIXIMAB (SIMULECT®)

Two IV doses of basiliximab, a monoclonal antibody IL-2 receptor blocker, may be given with subsequent islet transplants and second attempts at initial transplant. If basiliximab is administered, the first dose will be 20 mg and will be given within two hours prior to islet transplant on the day of islet transplantation. The second dose will be given on Day 4 after the transplant.

If a third transplant is deemed necessary and performed between 30 and 70 days after the second transplant, no additional doses of basiliximab will be given.

If a third islet transplant is deemed necessary and performed more than 70 days after the third transplant (see indication for subsequent transplants), both doses of basiliximab will be repeated.

5.4 Concomitant Medications

5.4.1 Immunosuppressive / Anti-Inflammatory Therapy

Etanercept (Enbrel®) will be administered at a dose of 50 mg IV on day 0 (1 hr prior to transplant), and 25 mg sc on days +3, +7, and +10 post-transplant.

Methylprednisolone (Solu-Medrol®) will be administered at a dose of 1 mg/kg IV one hour prior to and repeated midway through the first ATG infusion only (*i.e.* on day –2).

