1.3.3.2 Methylprednisolone (Solumedrol®)

Methylprednisolone is a synthetic glucocorticoid with potent anti-inflammatory and immunosuppressive properties that has been approved by the FDA for prevention and treatment of rejection in organ transplant recipients. This drug will be administered at a dose of 1mg/kg IV 1 hour prior to and as needed through the first ATG infusion only (i.e. on day -2). Patients will not receive any additional doses of this drug.

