1.5.4.2 Methylprednisolone (Solumedrol[®])

Methylprednisolone is a synthetic glucocorticoid with potent immunosuppressive properties that has been approved by the FDA for prevention and treatment of rejection in organ transplant recipients. It has also been approved for treatment of several autoimmune and rheumatologic disorders. This drug will be administered at a dose of 1mg/kg I.V. 1 hour prior to and as needed through the first ATG infusion only (i.e. on day -2). Patients will not receive any additional doses of this drug. Side effects are usually minor and self-limited during a short treatment course but may include hyperglycemia, hypertension, euphoria, visual disturbances, anaphylactic reactions, nausea and vomiting.

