In rare instances, anaphylaxis has been reported with Thymoglobulin® use. In such cases, the infusion should be terminated immediately. Medical personnel should be available to treat subjects who experience anaphylaxis. Emergency treatment such as 0.3 mL to 0.5 mL aqueous epinephrine (1:1000 dilution) subcutaneously and other resuscitative measures including oxygen, IV fluids, antihistamines, corticosteroids, pressor amines, and airway management, as clinically indicated, should be provided. Thymoglobulin® or other rabbit immunoglobulins should not be administered again for such subjects.

RABBIT ANTI-THYMOCYTE GLOBULIN-INDUCED CYTOKINE RELEASE

Thymoglobulin® infusion may cause cytokine release-related fever and chills. To minimize these, the first dose should be infused over a minimum of 6 hours into a high-flow vein. Also, premedication with corticosteroids (solumedrol, 1 mg/kg IV), pentoxifylline, acetaminophen, and/or an antihistamine will be provided in order to minimize the reaction incidence and/or intensity. At any sign of the above reaction, slowing the infusion rate by 50% will also occur.

NEUTROPENIA

Neutropenia is an expected consequence of the administration of several medications in this protocol. Subject safety is of utmost importance. Clinical treatment decisions take precedence over recommended guidelines.

If a subject's absolute neutrophil count is less than 1000 cells/ μ L and the subject is afebrile, then the following will be done:

- Reduce ATG by 50%.
- Test for CMV and if negative hold valganciclovir.
- Reduce trimethoprim/sulfamethoxazole to 80 mg/400 mg 3 times per week or hold trimethoprim/sulfamethoxazole.
- Review and obtain current sirolimus trough levels and consider dosage adjustment if trough levels are > 12 ng/dL (please refer to Appendix 1, SOE, for additional information).
- If subject is using mycophenolate mofetil or mycophenolate sodium in lieu of sirolimus, consider dose reduction.
- Consider administration of G-CSF.
- Monitor temperature BID.
- Follow-up within 48-72 hours to obtain repeat CBC with differential, subject symptoms, and measured temperatures.

If a subject's absolute neutrophil count is less than 1000 cells/ μ L and the subject is febrile, then the following will be done:

- Obtain Infectious Disease Consult.
- Obtain CMV antigenemia or PCR for CMV.
- Hold rabbit ATG.
- Hold valganciclovir and trimethoprim/sulfamethoxazole.

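### For the first ATG infusion, a further methylprednisolone dose is conditional in sections 1.3.3.2, 1.5.4.2 and 5.3.1 but scheduled for everyone in section 5.4.1

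*Combined protocol and SAP*

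**What the plan says.** Four sections of the combined protocol and SAP give the methylprednisolone rule for the first ATG infusion on day -2.

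- Section 1.3.3.2 (background): "1mg/kg IV 1 hour prior to and as needed through the first ATG infusion only".
- Section 1.5.4.2 (risks): "1mg/kg I.V. 1 hour prior to and as needed through the first ATG infusion only".
- Section 5.3.1 (initial transplant, premedication list): "1 mg/kg IV one hour prior to and as needed through the first ATG infusion only".
- Section 5.4.1 (concomitant medications): 1 mg/kg IV, "one hour prior to and repeated midway through the first ATG infusion only".

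Sections 1.3.3.2 and 1.5.4.2 both close with the sentence "Patients will not receive any additional doses of this drug".

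Two other places mention the premedication without any repeat. Section 1.3.3.1 lists methylprednisolone among drugs that "will be administered as premedications 1 hour prior to the first dose of rabbit ATG". The cytokine-release paragraph of section 5.8.2 refers to "premedication with corticosteroids (solumedrol, 1 mg/kg IV" and stops there.

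**The concern.** The first three sections make a dose after the opening one depend on need. Section 5.4.1 makes it part of the schedule. A site that writes orders from 5.3.1 gives an untroubled subject one dose; a site that writes them from 5.4.1 gives the same subject two.

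What is at stake is uniform administration and the ability to judge it. Section 5.8.2 asks for treatment modifications not directed by the protocol to be reported as deviations. Here, leaving out the midway dose follows 5.3.1 and departs from 5.4.1, while giving it without need does the reverse. Section 7.6.2 also makes a third transplant depend on a finding of no relevant protocol deviations at the site, so an instruction that cannot be followed in both places is worth clearing up.

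**Working it through.** No figure in the plan depends on this point, so there is nothing of the plan's own to reproduce. The check is a comparison of text followed by simple dose arithmetic.

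**Step 1. Is the repeat conditional or scheduled?**

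| Section | Before the infusion | During the infusion |
|---|---|---|
| 1.3.3.2 | 1 mg/kg, one hour before | as needed; no size, number or maximum |
| 1.5.4.2 | 1 mg/kg, one hour before | as needed; no size, number or maximum |
| 5.3.1 | 1 mg/kg, one hour before | as needed; no size, number or maximum |
| 5.4.1 | 1 mg/kg, one hour before | repeated midway; no condition |
| 1.3.3.1 | one hour before, no dose given | not mentioned |
| 5.8.2 | 1 mg/kg | not mentioned |

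**Step 2. Could the two wordings be loose synonyms?** The premedication list in 5.3.1 argues against it. Acetaminophen and diphenhydramine are to be given half an hour before and again midway through the infusion. Methylprednisolone, the next item, gets the as-needed wording instead. Within one list, then, midway marks a scheduled repeat and as-needed marks a conditional one. Section 5.4.1 applies the scheduled form to methylprednisolone.

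**Step 3. Does one section outrank the other?** Both 5.3.1 and 5.4.1 belong to chapter 5, the treatment regimen. No statement of precedence appears.

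**Step 4. Size of the gap.** Total on day -2 = number of doses × 1 mg/kg, taking the repeat in 5.4.1 to be a second full dose.

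- Subject with no need for a further dose, under 5.3.1: 1 × 1 mg/kg = 1 mg/kg.
- The same subject under 5.4.1: 2 × 1 mg/kg = 2 mg/kg.
- Illustration at the 90 kg upper weight limit (section 3.2, criterion 1): 1 mg/kg × 90 kg = 90 mg against 2 mg/kg × 90 kg = 180 mg. This is the heaviest eligible subject, not a typical one.
- Subject with a need: 1 mg/kg plus an unstated amount under 5.3.1. That total may fall below, equal or exceed 2 mg/kg, so no difference can be computed.

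**Step 5. Scope.** The instruction is tied to the first ATG infusion. Table 1 reserves ATG for the initial transplant, so later transplants without ATG are outside this point.

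**The case against.** The best case on the other side accepts that the wording should be tidied and says that little follows from it. Most of that is right, and it rules out four stronger readings that a reader might infer.

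- **A flat two-fold dose difference for every subject.** Not supported. The contrast of 1 with 2 mg/kg holds only where no further dose is needed, and only if the repeat is a full dose, which 5.4.1 does not spell out.
- **A ban on the midway dose in the sentence "Patients will not receive any additional doses of this drug".** Not supported. In 1.3.3.2 and 1.5.4.2 it follows a sentence that already allows further drug during that infusion, so it naturally bars doses afterwards. Section 5.4.1 carries the same restriction to the first infusion and agrees with it.
- **A clash with the prednisone limit of 10 mg/day.** Not supported. That limit concerns maintenance therapy (section 3.1, criterion 6; section 4) and prohibited medication (section 5.6), and 5.6 exempts what the protocol itself specifies.
- **Distortion of the day 75 result or the comparison with CIT-06.** Not shown. The CIT-06 steroid instruction is not in the documents, and nothing in them links one extra premedication dose to insulin independence at day 75. Steroid exposure on day -2 also varies for other reasons: as-needed dosing is allowed, and 5.3.1 adds hydrocortisone 20 mg when ATG is given through a peripheral line.

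These objections limit the consequences. They do not remove the contradiction, because a repeat cannot be both conditional and unconditional for the same infusion.

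**Conclusion.** The point stands as an internal inconsistency of minor weight. For the first ATG infusion, three sections make a further methylprednisolone dose conditional and one schedules it, with no rule of precedence. The difference is 1 mg/kg (2 − 1) for a subject with no clinical need for more, assuming that the repeat in 5.4.1 equals the opening dose. For other subjects it is undefined, because the as-needed wording has no stated size or cap. The practical consequence is that sites can treat the same subject differently while each follows an operative section, and neither course can be classed clearly as compliant or deviant. No endpoint definition, power, type 1 error or sample-size figure changes.

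**What to change.** The sponsor should state which instruction is intended and align sections 1.3.3.2, 1.5.4.2, 5.3.1 and 5.4.1 so that one remains. Sections 1.3.3.1 and 5.8.2 should be checked against it, since both describe the premedication without a repeat. The reconciled text should make clear whether any dose during the infusion is conditional or scheduled, and how large it is. Which rule is right is a clinical decision for the sponsor, and this review proposes none. The cost is an edit to protocol wording and to any site order sets drawn from it; no analysis or sample size needs reworking.
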